4.2 Exclusion Criteria

- Those with significant cardiorespiratory disease, other than COPD, considered the primary cause of their breathlessness/high SABA use.
- Those with a COPD exacerbation requiring oral corticosteroids and/or antibiotics and/or hospitalisation within 4-weeks before recruitment (taken from last day of exacerbation treatment).
- Those with a planned pulmonary rehabilitation attendance during the study (pulmonary rehabilitation referral will be offered on completing trial participation if appropriate).

4.3 Participant Identification and Screening

Participants will be identified by study sites. Participant identification centres (PICs) will be considered if requested by the participating sites, particularly if a PIC would support inclusion of minority or underserved communities. Participants will be identified and approached in two ways:

- 1. Participants will be identified by their usual care team during delivery of usual care, or through electronic health record search, and provided with information about the study in one of the following ways: 1) In person, e.g. during a clinic attendance, 2) Verbally, e.g. during a phone or video consultation, 3) In writing, e.g. via postal services and/or digital platforms. Each method of information delivery should be conducted in accordance with sites usual practice and standard operating procedures (SOPs). Following this, consent will be sought to share the participant's details with the research team, who will provide further information about the study, the participant information sheet (PIS), and answer any questions relating to the study.
- 2. Potential participants that have previously provided consent for their details to be retained on a clinical trial or research database for the purpose of future research participation will be contacted directly by the site research team and provided with study information, including the PIS, and provided with an opportunity to ask questions.

Written informed consent will be obtained for all participants in accordance with Good Clinical Practice.

All patients who are approached for the study will be invited to complete a short 'Trial Invitation Experience Survey' assessing their experience of recruitment and their reasons for why they consented to participate or declined.

| Confidential | Protocol | | | | | |
|--------------|-------------|--------------------------|---------------|--|--|--|
| Connacitiai | IRAS 318320 | Version No. 1.1 29.08.23 | Page 17 of 57 | | | |

Participants that fail screening on first attempt will be eligible for re-screening, provided the reason for screen failure is resolved prior to completion of study recruitment. This does not apply to cases where screen failure is related to SABA-use during the prior 12-months being below the threshold for study inclusion. In these case, re-screening will not be permitted. Those participants who become eligible following re-screening will be assigned with a new SIN. Participants that screen fail will be replaced.

4.4 Participant Withdrawal

Participants have the right to withdraw from treatment or the study at any time. The investigator(s) or sponsor may withdraw patients from treatment or the study, only if indicated by a safety or clinical issue, or where a deviation from study protocol has occurred.

Participants should remain in the study for follow-up unless they request to fully withdraw. All data up to the point of withdrawal will be retained. Both participants who withdraw, or complete, will be invited to complete a short survey e.g., The Study Experience Survey. This survey is designed to understand participants' experience of study participation, any reasons for withdrawal, and to indicate their willingness to participate in a future interview.

In the event of participant withdrawal, the Investigator(s) will promptly explain to the participant that their involvement in the study will discontinue and explain why. In the cases where medical intervention is warranted, investigators will facilitate provision of medical treatment and/or other necessary measures deemed appropriate for the participant. A participant who does not return for follow-up visits but who has not consented to complete a study experience survey will be followed up by phone or other means, as far as is possible, to offer them the opportunity to give a reason for withdrawal; which will be recorded in the CRF. It will be made clear to participants that they do not have to explain their withdrawal, if they do not wish to do so.

As well as self-withdrawal, other primary reasons for participants withdrawing from the study will be due to: AE(s), participant deterioration of disease, participant death, participant lost to followup, significant protocol violation. All provided reasons for study discontinuation will be collected on the participants CRF.

Protocol

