3. STUDY DESIGN

Multicentre, parallel-group, open-label, randomised controlled, hybrid Type-I effectivenessimplementation feasibility study. Patients will be randomised to either usual care or the FanFIRST intervention in a 1:1 ratio using random permuted blocks. Randomisation will be stratified by site and based on self-reported HHF usage (any reported HHF-use) within the past month.

Taking an overall effectiveness research perspective, consistent with the MRC's updated framework for developing and evaluating complex interventions²²²², the study incorporates a theory-based approach to assess how processes, impact mechanisms and contextual factors shape outcomes²³²³²³.

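### Section 4.4 keeps participants in follow-up unless they ask to leave, yet lets staff end study participation for any protocol deviation

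*Protocol*

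**What the plan says.** All the text at issue is in Protocol section 4.4.

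- **Staff power.** The sponsor or an investigator "may withdraw patients from treatment or the study, only if indicated by a safety or clinical issue, or where a deviation from study protocol" took place.
- **Follow-up rule.** "Participants should remain in the study for follow-up unless they request to fully withdraw".
- **What withdrawal means.** The investigator "will promptly explain to the participant that their involvement in the study will discontinue and explain why".
- **Data.** "All data up to the point of withdrawal will be retained".
- **Closing list.** Besides self-withdrawal, the reasons for leaving the study are given as "AE(s), participant deterioration of disease, participant death, participant lost to followup, significant protocol violation".

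Section 3 describes the design as "Multicentre, parallel-group, open-label, randomised controlled", with allocation "in a 1:1 ratio using random permuted blocks". Section 6.2.1 sets the proposed primary clinical outcome as change in mean daily SABA use from baseline to days 56 to 84. Section 11 plans between-group effect sizes with 95% confidence intervals and no formal tests. Section 12.2 makes retention a traffic-light criterion: green above 75%, amber 60 to 75%, red below 60%.

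**The concern.** Two sites could apply opposite rules and both be following the protocol. One keeps a non-compliant participant in follow-up to day 84. The other withdraws the same kind of participant at day 40 because a deviation occurred. The decision is made after randomisation by people who know the arm, and it stops collection of the outcome that the definitive trial is expected to use.

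Three things are at stake: whether the days 56 to 84 data are complete, whether the effect sizes compare the groups as randomised, and whether the retention figure reflects participants' willingness to stay or the trial's own decisions.

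**Working it through.** No calculated figure in the protocol bears on this point, so the check is mainly a comparison of text.

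**1. Who may end follow-up.** The follow-up rule admits one exception, a request from the participant. The staff power adds two more: a safety or clinical issue, and a deviation. The sentences conflict unless one of them is about something else.

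**2. Can the staff power be read as covering treatment only?** No. It names the study as well as treatment, and the section says that on withdrawal the participant's involvement ends. Sections 5.1 and 5.2 also describe the intervention as a session of about 10 minutes, given straight after randomisation, while the usual-care arm receives it only at the final visit. After day 0 there is little treatment left to stop, so in practice the power acts mostly on study participation.

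**3. Thresholds for the same ground.** The staff power refers to a deviation without qualification. The closing list refers to a significant violation. Section 13.9 requires deviations to be documented and reported, and section 7.4.3 records unsensored inhaler use with the hours or days missed. Neither calls for withdrawal, and neither limits the power in 4.4.

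**4. Effect on the outcome window.** Participants are randomised at day 0. Withdrawal on day t < 56 leaves no data in the window. Withdrawal on day t between 56 and 84 leaves about (t − 56) of 28 days. At day 70, for example, that is 14/28, or half.

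**5. Route to selective removal.** Sites do not see sensor counts (sections 6.2.1 and 10.2), so they cannot select on the SABA data directly. They do know the arm, see clinical state, ask about unsensored use (7.4.3) and are alerted after 7 days without syncing (10.2). Clinical state and non-compliance can plausibly relate to SABA use and to arm.

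**6. Retention.** Inputs are the section 12.2 bands and the planned 80 participants, the latter being an assumption about the denominator.
- Green: 0.75 × 80 = 60, so at least 61 must be retained and at most 80 − 61 = 19 may leave for any reason.
- Red: 0.60 × 80 = 48, so 47 or fewer retained, meaning 80 − 47 = 33 or more have left.

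Every staff-initiated exit uses up part of the same allowance as participant drop-out.

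**7. Baseline variability.** Objective 2 and section 6.2.1 take SABA variability from days −28 to 0, before randomisation, and data up to withdrawal are kept. Later withdrawals do not affect it.

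**The case against.** The staff power is permissive and limited to stated grounds. Other sections point towards keeping unwell participants: COPD admissions are expected events (9.4), adverse events are followed until resolution or a decision to stop (section 9), and admissions are outcome data (6.2.2). Reasons for discontinuation go on the CRF, so exits could be separated afterwards. No formal tests are planned. All of this stands and limits the weight of the point, but none of it reconciles the sentences in 4.4.

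A reader might infer more than the text supports, in four ways.

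- **That adverse events and deterioration are express staff grounds for removal.** They appear among "other primary reasons for participants withdrawing from the study will be due to: AE(s), participant deterioration of disease, participant death", which does not say who initiates the exit. The staff wording about a clinical issue could cover them, but that is an inference.
- **That staff could remove high users.** Sites are blinded to sensor counts. One nominated central person sees usage and can raise fidelity problems with sites (10.2), which is a much narrower route.
- **That the standard deviation passed to the definitive trial is lowered.** The protocol takes that variability from baseline.
- **That a particular bias can be stated.** Suppose 85% of each arm use 7 actuations a day and 15% deteriorate to 12. The true mean is 0.85 × 7 + 0.15 × 12 = 7.75. Removing all deteriorators in one arm gives 7.00. Removing half in the other gives (0.85 × 7 + 0.075 × 12)/0.925 = 7.41, a difference of 0.41. With equal removal in both arms the difference is 0. The whole result comes from the assumed imbalance, for which the protocol gives no basis. The same scenario averages (15 + 7.5)/2 = 11.25% exits, so an assumed retention of 90% becomes 78.75%, or 63 of 80, which is still green.

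**Conclusion.** The contradiction within section 4.4 is definite and needs no assumption. It permits, but does not require, allocation-aware removal that cuts off the days 56 to 84 outcome, and it mixes trial-imposed exits into a stop-go measure. The bias in the effect sizes is a possibility whose direction and size cannot be derived from the document. It would require exits related to SABA use and differing between arms.

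It would be too strong to say that the retention criterion ceases to measure feasibility, because recorded reasons allow exits to be separated if the report does so. The 19-exit allowance depends on 80 being the denominator. For a feasibility trial without formal testing this should be corrected, but it does not undermine the design.

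**What to change.** Reconcile the sentences in section 4.4:

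- Separate stopping the intervention from ending follow-up and data collection, and say which of the two each listed reason refers to.
- Remove protocol deviation or violation as a ground for ending study follow-up. Record and report it under section 13.9 and the section 7.4.3 fidelity questions, and continue sensor recording and visits to day 84 where the participant agrees.
- Report staff-initiated and participant-initiated exits separately against the retention criterion in section 12.2.

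Which safety or clinical grounds may end participation is the sponsor's decision. The request is only that they be stated once and consistently with the follow-up rule.

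The cost is a few sentences, a field on the withdrawal CRF for who initiated the exit, and a few more follow-up visits.

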5. STUDY INTERVENTION

5.1 Summary

Intervention

All participants will receive *usual care* as per local guidelines. This will include, but not be limited to, inhalers (minimum dual long-acting bronchodilator therapy), oral medications and oxygen therapy when indicated. Participants' use of breathlessness self-management strategies will be recorded at baseline and throughout the study.

Participants randomised to **the FanFIRST intervention** will be given a rechargeable HHF. Verbal and written instructions in the HHFs use, guidance on positions/breathing techniques and exercises to relieve breathlessness; and written information about managing anxiety to improve breathlessness will also be provided. The intervention is designed to be deliverable by a clinician during a standard consultation, taking ~10 minutes to complete (further details specified in Table 2 FanFIRST Summary Intervention components mapped using TIDieR checklist).

5.2 FanFIRST Intervention Delivery

The FanFIRST intervention will be delivered immediately following participants' successful randomisation to the FanFIRST arm of the study⁺; after completion of baseline assessments. The intervention can be delivered by clinicians (nurses, doctors and/or allied health professionals) within the site clinical / research team that have received appropriate training and have had FanFIRST intervention delivery delegated to them by the PI. A record of training and delegation of intervention delivery will be recorded on the appropriate logs.

Delivery of the FanFIRST intervention will be recorded using an intervention checklist to facilitate assessment of intervention fidelity (see section 5.3 for further details).

⁺ Participants randomised to receive usual care will receive the intervention during the final study visit, following completion of all other study measures and activities.

5.3 Intervention Fidelity

Formal training for FanFIRST intervention delivery will be provided for clinicians at study sites by members of the research team experienced in delivery of the intervention.

Table 2 FanFIRST Summary Intervention components mapped using TIDieR checklist

| Component | Why | What | Who | How | Where | When/How much | Tailoring & modifications | How well |
|---------------------------|---|---|--|---|--|--|--|--|
| Clinician Training | Clinician lack of knowledge and poor communication about breathlessness and its management with patients ⁴⁴⁵ Training programmes with Breathing, Thinking, Functioning (BTF) model and non- pharmacological interventions improves clinicians knowledge and confidence to manage breathlessness ⁴⁶ | Teaching session Chronic breathlessness and management with BTF and non- pharmacological interventions (a toolkit) SABA overuse Demonstrate, rationale, and practice delivery intervention components –a), b), c) and d) Materials On-line video, paper copy of training session and links to resources | Clinicians on the research team | Delivery of face to face and/or on- line teaching session | AMB, University of Hull and/or on-line via Zoom. | Before start of recruitment 20-30 minutes max training session | If face to face not possible then on- line teaching session Video resource of teaching session on- line | Breathlessness knowledge and skills assessment, feedback form, interviews |
| Resting Position (a) | Forward lean position to maximise ventilation 4749 | Procedure: Demonstration of comfortable position, forward lean, and flop and drop shoulders | Doctor, nurse | Delivery face to face | Outpatient hospital, GP practice | Beginning of trial. 2 minutes | Modify resting position to patient preferences | Fidelity Patient feedback from interviews clinician. |
| Breathing exercise (b) | Lengthen breath out e.g. pursed lip breathing (PLB) or "breathing rectangle". ⁴⁷ ⁵⁰ increases end-expiratory pressure and reduces breathlessness ^{44,50} . Evidence to support use with COPD ⁵¹ | Procedure: Demonstration of "breathing rectangle" and PLB Focus on lengthening breath out | Doctor, nurse | Delivery face to face | Outpatient hospital, GP practice | Beginning of trial. 2 minutes | Modify breathing exercises to patient preferences | Fidelity Patient feedback from interviews clinician. |
| Hand-held fan (c) | Fan provides relief of breathlessness and reduces recovery time from exercise ²¹ 2231 Fan delivery important ³² Patient fan use instead of a SABA inhaler ²³ 31 | Procedure: Demonstration of fan Explain fan mechanism and use Patient fan practice | Doctor, nurse | Delivery face to face | Outpatient hospital, GP practice | Beginning of trial. 3 minutes | Modify fan position, airflow speed to patient preference | Patient feedback from interviews clinician. |
| Thoughts (d) | Relationship between thoughts – anxiety and breathlessness. ^{53,54} BTF model anxiety can perpetuate breathlessness. ⁵⁵ and ATS statement endorses use of action plan ⁶ . | Procedure: Listen and acknowledge patients' thoughts about breathlessness Action plan for anxiety Materials Paper information leaflets with pictures to guide on components a), b), c), and d) Laminated Action plan* Link to on-line resources | Doctor, nurse | Delivery face to face | Outpatient hospital, GP practice | Beginning of trial. 5 minutes | Modify to patient thoughts and what they believe about breathlessness | Fidelity Patient feedback from interviews clinician. |

*Laminated Action Plan for Breathlessness I am going to lean forward (a) Focus on breathing out for longer (b) I am going to use my fan (c) I can do this – I am ok (d) Delivery of the core components of the breathlessness intervention should be documented by the delivering clinician within the participant's medical record and eCRF (Appendix C). If a core component of the breathlessness intervention has not been delivered, then the reason for this must be documented in the participant's medical record and eCRF. Delivery of the intervention in accordance with the protocol will be assessed during monitoring visits.

During each participants study visit, both groups will be asked to report any breathlessness management strategies that they have been instructed in and/or have used as part of their usual care and therefore not as a result of the studied intervention.

6. OUTCOMES AND MEASURES

This is a feasibility trial and therefore the primary outcome measures address areas of uncertainty relating to design and delivery of a Phase 3 randomised controlled trial. These outcomes are termed feasibility outcomes. As part of this trial a number of clinical outcomes will also be evaluated.

Eligibility criteria will be assessed at day -28 to ensure only eligible participants will proceed with baseline assessments. Pre-baseline, assessments will be undertaken on day -28. Baseline monitoring of SABA usage via smart inhaler will be undertaken over 28-days (from day -28 to day 0) to allow for adequate baseline SABA-use data collection. Questionnaires will be completed on Day -28 and Day 0 to establish measure stability; with Day 0 considered the baseline visit, baseline end, and start of study. Spirometry (post-bronchodilator) will be performed at day -28 (or as soon after as possible depending on availability/infection control procedures at sites) to confirm eligibility and assess COPD severity. Where spirometry cannot be completed at day -28 due to a lack of availability at site and/or imposed local infection control procedures, participants will proceed with SABA use monitoring, with spirometry completed and eligibility confirmed, prior to undertaking further baseline assessments at day 0. Participants will be randomised on Day 0 with assessments every 28-days thereafter to complete 84-days follow-up.

6.1 Feasibility Outcomes

The feasibility outcomes and when assessments will take place are outlined in Table 3. The feasibility and fidelity of the intervention will be measured through adherence in delivery and uptake of the intervention (as a whole and individual intervention components) as documented in the eCRF. Overall intervention acceptability will be assessed via qualitative interviews.

Table 3 Feasibility outcomes and timing of assessments

| Recruitment | Data quality and integrity | Outcomes ⁺ |
|---------------------------------|----------------------------------|------------------------------|
| • Eligibility to consent ratio; | Completion of clinical | Acceptability of proposed |
| recruitment rate (per-site | outcomes (questionnaires | outcomes (assessed |
| and aggregated) | and other assessments) at | through qualitative |
| • Screen failure points (SFPs) | each time point | interviews) and integrity of |
| Participant retention/ | Amount/patterns of | outcome data |
| follow-up rates at each | missing data for the study | |
| time point | measures. | |
| | | |
| | ASSESSED AT: | |
| Consent/Screening visit, | (Baseline [D0], Visit 1 [D28±3], | |
| Baseline [D0], Visit 1 [D28±3], | Visit 2 [D56±3] and Visit 3 | |
| Visit 2 [D56±3] and Visit 3 | [D84±3]) | |
| [D84±3]. | | |

⁺A traffic light system will be used for feasibility outcomes (see section 12.2).

6.2 Clinical Outcomes

6.2.1 Primary Outcome

The proposed primary outcome is:

 Change in mean daily SABA use from baseline (days -28-0) at days 56 to 84 (see trial flow chart).

Smart inhaler technology* (Propeller Health, USA) will be used to objectively count SABA actuations each day. Baseline data will inform intra- and inter-individual SABA use variability and optimal monitoring duration for the definitive trial. Daily SABA use will be recorded throughout the trial to enable evaluation of change in use and any potential degradation of intervention effect over-time.

*The Propeller sensor attaches to participants' own SABA inhaler and automatically records each inhaler actuation. A range of sensors are available to fit different inhaler devices as necessary. Each participant will be provided with 2 sensors to account for patients often having more than 1 SABA inhaler. Participants will be asked to only use SABA inhalers that have the sensors attached during the study. Participants will be provided with training in use of the sensor and in transferring the sensor from one inhaler to another when their SABA runs out. Participants will be reminded to change over sensors (if necessary) during each study visit.

Sensor SABA use data will not be made available to participants or site teams during the course of the trial to prevent this influencing SABA use through biofeedback. However, HHTU and sites will have access to a Clinician Portal (provided by Propeller Services) where they will be able to see enrolled participants, identified by their SIN, for administrative purposes. Syncing of inhaler sensors will be monitored centrally by HHTU, with site teams alerted in the event of apparent failure of data recording for 7 days.

